## 6. TREATMENT PLAN

### 6.1 VIR-7831 administration

VIR-7831 will be given intravenously as a single dose of 2,000 mg infused over approximately 60 minutes. A 500 mg single dose was used in the phase 3 COMET-ICE study and is the dose authorized under the EUA for early treatment. However, the 500 mg dose has reduced *in vitro* neutralization potency against the Omicron BA.2 subvariant which has emerged as the predominant variant of SARS-CoV-2 in the United States. An increased dose of 2,000 mg is predicted to rescue neutralization potency against Omicron BA.2 and will be used for the remaining 30 subjects in this study. A lead-in phase will consist of the first ten participants infused with the 2,000 mg dose. Lead-in phase participants will have a 120-minute post-infusion observation period, which is increased from the 60-minute monitoring period used for the previous 20 participants who received the 500 mg dose. If no infusion-related reactions (grade 3 or above) or serious adverse events are noted between 60-120 minutes post-infusion, the monitoring period may be shortened to 60 minutes. The mAb will be administered within seven days prior to the planned start of pre-transplant conditioning, and the mAb will be infused at least 24 hours prior to the start of conditioning, i.e. mAb infusion will occur within 1-7 days prior to conditioning). If conditioning is unexpectedly delayed by > 14 days after administration of VIR-7831, the subject can stay in the study but will not count towards the target sample size and will be excluded from the primary analysis. This would allow continued safety monitoring and analysis of secondary and exploratory objectives. Vials with the mAb will be stored between 2 and 8°C in the investigational drug service (IDS) pharmacy at FHCC.

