### **6.1.3 Acute infusion reactions.**

After injection, the first ten participants receiving the 2,000 mg dose will be observed for 120 minutes for any symptoms (none are expected). If there are no infusion-related reactions (grade 3 or above) or serious adverse events, the monitoring period for the next twenty participants can be shortened to 60 minutes. Participants will be encouraged to contact the investigator if there are any concerns of adverse events following the infusion. A physician, nurse, nurse practitioner, and/or physician's assistant will assess for initial infusion reactions and record solicited adverse events. IV infusion will be administered in the clinic with staff trained in emergency care & resuscitation procedures & emergency care kit on hand during treatment & post therapy observation periods. Vital signs will be monitored at the beginning and end of the 60-minute IV infusion. Subjects will be clinically observed for at least 60 minutes (120 minutes for the lead-in phase) post-infusion during the observation period. Vitals will be measured every hour during the observation period.

If a participant experiences a Grade 2 infusion-related reaction, nursing will be instructed to pause the infusion. The infusion may subsequently resume at a slower pace of infusion, at the investigator's or clinician's discretion, and/or after symptomatic treatment (e.g., antihistamines, IV fluids). Investigators and clinicians will be instructed to discontinue IV infusions for participants who develop Grade 3 or higher infusion reactions. After infusion, study participants will be provided with investigators' contact information and asked to contact the study team if they experience subsequent adverse events, to collect unsolicited adverse events and SAEs.

Grading system from NCI CTCAE 5.0

**Grade 1:** Mild transient reaction; infusion interruption not indicated; intervention not indicated

**Grade 2:** Therapy or infusion interruption indicated but responds promptly to symptomatic treatment (e.g., antihistamines, NSAIDS, narcotics, IV fluids); prophylactic medications indicated for <=24 hrs

**Grade 3:** Prolonged (e.g., not rapidly responsive to symptomatic medication and/or brief interruption of infusion); recurrence of symptoms following initial improvement; hospitalization indicated for clinical sequelae

**Grade 4:** Life-threatening consequences; urgent intervention indicated

**Grade 5:** Death

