## 7. POTENTIAL RISKS AND TOXICITY MONITORING

VIR-7831 has been administered in a Lead-In study phase (based on the 1:1 randomization scheme; overall N = 21) and was generally well tolerated as a single IV infusion at a dose of 500 mg. No subjects died or discontinued from the study due to adverse events (AEs). Based on safety assessment of unblinded Lead-In data, the Independent Data Monitoring Committee (IDMC) recommended initiation of the Expansion study phase. The ongoing Phase 1/2/3 double-blind, placebo-controlled, randomized study enrolled 1,057 non-hospitalized patients with COVID-19 (COMET-ICE). The safety of VIR-7831 is primarily based on an interim analysis from 868 patients through Day 15. All patients received a single 500-mg infusion of VIR-7831 (N = 430) or placebo (N = 438). Two patients experienced treatment interruptions due to infusion site extravasation; infusion was completed for each. Infusion-related reactions, including immediate hypersensitivity reactions, have been observed in 1% of patients treated with VIR-7831 and 1% of patients treated with placebo in COMET-ICE. Reported events that started within 24 hours of study treatment were pyrexia, chills, dizziness, dyspnea, pruritus, rash, and infusion-related reactions; all events were Grade 1 (mild) or Grade 2 (moderate). One case of anaphylaxis was reported following VIR-7831 infusion in a study in hospitalized patients; the infusion was immediately discontinued, and the patient received epinephrine. The event resolved but recurred within 2 hours; the patient received another dose of epinephrine and improved with no additional reactions. Other serious infusion-related reactions (including immediate hypersensitivity reactions) reported following VIR-7831 infusion in the hospitalized study included Grade 3 (serious) or Grade 4 (life-threatening) bronchospasm and shortness of breath. These events were also reported following infusion of placebo. The most common treatment-emergent adverse events observed in the VIR-7831 treatment group in COMET-ICE were rash (2%) and diarrhea (1%), all of which were Grade 1 (mild) or Grade 2 (moderate). No other treatment-emergent adverse events were reported at a higher rate with VIR-7831 compared to placebo. The 250 mg and 500 mg IM doses were evaluated in COMET-TAIL (NCT04913675). So far, reported AEs were not found to be dose-dependent, suggesting a large increase in rate of AEs with 2000 mg IV of sotrovimab is unlikely. We will monitor all subjects for at least 60 minutes (120 minutes for lead-in participants) post-infusion.

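### The condition for shortening post-infusion observation at 2,000 mg has a 60-120 minute window in Section 6.1 and no window in Section 6.1.3

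*Combined protocol and SAP*

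**What the plan says.** Section 6.1 of the combined protocol and SAP sets up a lead-in of the first ten participants at 2,000 mg, with 120 minutes of observation after the infusion, "which is increased from the 60-minute monitoring period used for the previous 20 participants who received the 500 mg dose". It then gives the rule for relaxing this: absent grade 3 or higher infusion-related reactions, and if no "serious adverse events are noted between 60-120 minutes post-infusion, the monitoring period may be shortened to 60 minutes".

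Section 6.1.3 covers the same ground. It begins "After injection, the first ten participants receiving the 2,000 mg dose will be observed for 120 minutes for any symptoms", and the next sentence makes shortening to 60 minutes conditional on there being "no infusion-related reactions (grade 3 or above) or serious adverse events, the monitoring period for the next twenty participants can be shortened". It gives no time window and does not refer back to 6.1.

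Section 7 repeats only the durations: "We will monitor all subjects for at least 60 minutes (120 minutes for lead-in participants) post-infusion". Footnote G of Appendix A deals only with vital signs. Nothing in the document says which statement of the condition prevails.

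**The concern.** Someone applying Section 6.1 looks only at the second hour after infusion. Someone applying 6.1.3 as written looks at any qualifying event, and the sentence follows directly on the 120-minute observation. A severe reaction that came early and settled would be disregarded under one section and counted under the other.

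An early severe reaction is relevant to the second hour because it can come back. Section 7 describes an anaphylaxis after VIR-7831 in hospitalized patients. The infusion was stopped at once, and then: "The event resolved but recurred within 2 hours; the patient received another dose of epinephrine". Section 7 does not time this against the end of infusion, so it shows that recurrence is possible and nothing more.

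At stake is how long the remaining participants at the higher dose are watched. Section 7 also says that no PK or immunogenicity data yet exist for 2,000 mg given intravenously.

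**Working it through.** This is a comparison of two rules, and the plan has no figure of its own to reproduce.

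**Inputs**
- Participants to receive 2,000 mg: 30 (Section 4)
- Lead-in participants: 10 (Section 6.1)
- Participants to whom the decision applies: 30 - 10 = 20, which matches the twenty named in 6.1.3
- Dose ratio: 2,000 / 500 = 4
- Infusion time: about 60 minutes; observation: 120 minutes, or 60 if shortened (Sections 6.1 and 6.1.3)

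**Applying each rule to the possible lead-in outcomes.** A qualifying event is a grade 3 or higher infusion-related reaction or an SAE.

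| Qualifying event in the ten lead-in participants | Section 6.1 | Section 6.1.3 |
|---|---|---|
| None | condition met | condition met |
| Only at 60-120 minutes after infusion | not met | not met |
| Early, and persisting or recurring at 60-120 minutes | not met | not met |
| Only in the first 60 minutes after infusion | **met** | **not met** |
| Only during the infusion | **met** | **not met**, taking the absence of a window literally |

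The third row treats an event still present, or back again, in the second hour as noted there. That narrows the disagreement, because the Grade 3 definition in 6.1.3 includes prolonged reactions and "recurrence of symptoms following initial improvement", so some early severe reactions will reach into the second hour and be caught by both rules.

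The last row matters because 6.1.3 itself expects reactions while the drug is running: it pauses the infusion at Grade 2 and stops it at Grade 3 or higher. A reaction severe enough to stop the infusion, but resolved by the second hour of observation, would not count under 6.1.

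**Cost of the stricter condition, if triggered.** 120 - 60 = 60 minutes per participant, and 20 x 60 = 1,200 minutes = 20 participant-hours.

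**The case against.** The best defence is that 6.1.3 is a shortened restatement of 6.1. Both share the lead-in, the severity threshold, the SAE clause and the durations. Section 6.1 also supplies a logic: the second hour was added to the 60 minutes used at 500 mg, so the test is whether that hour detects anything. On this reading the fuller sentence supplies the missing window. That may be what was intended, but 6.1.3 does not say so, and it is the section staff would open when a reaction occurs.

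The defence does dispose of several stronger readings that a reader might infer:

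- *That the sections issue opposite instructions.* They do not. One says may and the other says can. Neither says 120 minutes must continue after an event, and keeping 120 minutes complies with both. The site is never forced to breach one section to follow the other.
- *That participants would go unprotected.* Every participant is watched for at least 60 minutes under either wording. Vital signs are taken hourly, trained staff and an emergency kit are at hand (6.1.3), and SAEs are reviewed as they occur, with team meetings at least weekly (Section 13.2).
- *That the anaphylaxis in Section 7 demonstrates the gap.* It does not. A recurrence falling at 60-120 minutes would block shortening under both rules.
- *That the chance of disagreement can be bounded from the 500 mg trial.* The documents give no grade 3 or higher rate at 2,000 mg. A bound from non-hospitalized COVID-19 patients at 500 mg would leave out other SAEs, the fourfold dose and transplant candidates.
- *That 6.1.3, having no window, also reaches SAEs days or weeks later.* Its position directly after the 120-minute observation, under a heading on acute infusion reactions, speaks against this.

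The difference between the two operative sentences remains, with no text to settle it.

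**Conclusion.** The point holds as a minor inconsistency in a safety rule, and it should be corrected. A grade 3 or higher infusion-related reaction or SAE outside the 60-120 minute window, which does not persist or recur within it, permits shortening under 6.1 but does not meet the condition in 6.1.3. The decision reaches 20 of the 30 participants at 2,000 mg and concerns one hour of observation for each. Enrolment, pharmacokinetic sampling, endpoints, sample size and analysis are unaffected.

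The conclusion rests on reading 6.1.3 as written. For events in the first hour after infusion this is the natural reading, given the sentence before it. For events during the infusion it rests on taking the missing window literally. How often the situation would arise cannot be estimated from the documents.

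**What to change.** Put one identical condition in Sections 6.1 and 6.1.3:

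> If none of the ten lead-in participants has a grade 3 or higher infusion-related reaction or SAE from the start of infusion through the end of the 120-minute post-infusion observation, observation for the next twenty may be shortened to 60 minutes.

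Naming the start of infusion is deliberate. A condition confined to the post-infusion period would disregard a reaction that stopped the infusion and then resolved. If the sponsor did intend the 60-120 minute window, copying it into 6.1.3 would also remove the inconsistency, but early events would then not count, and the protocol should say that this is meant.

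The wording should be settled before the lead-in is complete, so that the rule is not chosen with an event already known. Section 7 needs no change.

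The cost is one sentence aligned in two places and, only if the condition fails, at most 20 participant-hours of added observation.

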#### 6.1.1 Preparation of VIR-7831

VIR-7831 is manufactured in compliance with cGMP regulations. VIR-7831 is expressed in Chinese hamster ovary (CHO) cells using typical components for expression in mammalian cells. VIR-7831 drug product is provided as a sterile solution and contains no preservatives. Each single-use, 10 mL vial contains 500 mg of VIR-7831 (Gen2) at a concentration of 62.5 mg/mL as a clear liquid solution with a formulation of 20 mM histidine, 7% sucrose (w/v), 0.04% PS80 (w/v), 5 mM L-methionine at pH 6.0.

#### Product Storage:

The vials will be stored in the refrigerator at 2–8°C (35–46°F) at the IDS pharmacy and administered in the Infusion Services CTU. The mAb preparation does not contain preservatives and therefore should be used only once (no multiple entries into a vial).

#### 6.1.2 Infusion Protocol

VIR-7831 is provided in a single-use vial in an individual carton and labeled as required per country requirement. Under normal conditions of handling and administration, study drug is not expected to pose significant safety risks to site staff, but adequate precautions should be taken to avoid direct eye or skin contact and the generation of aerosols or mists. Parenteral drug products should be inspected for particulate matter and discoloration prior to administration, whenever solution and container permit. If evidence of such defects is observed, the product should not be used. Infusion will be performed either by inpatient nursing or by outpatient infusion center nursing.

- 1) The vial is equilibrated to room temperature for at least 15 minutes. Gently swirl the vial to mix without creating air bubbles. The IV solution can then be prepared using either empty or pre-filled sterile infusion bags as specified in the pharmacy manual.
- 2) Pre-infusion blood sample (approximately 10 mL) and nasal swab will be collected
- 3) After preparation of the injection site with an appropriate germicide, immediately inject the mAb intravenously. The mAb can be administered through a central line if the participant has one that is functional. The infusion duration is approximately 60 minutes.

### **6.1.3 Acute infusion reactions.**

After injection, the first ten participants receiving the 2,000 mg dose will be observed for 120 minutes for any symptoms (none are expected). If there are no infusion-related reactions (grade 3 or above) or serious adverse events, the monitoring period for the next twenty participants can be shortened to 60 minutes. Participants will be encouraged to contact the investigator if there are any concerns of adverse events following the infusion. A physician, nurse, nurse practitioner, and/or physician's assistant will assess for initial infusion reactions and record solicited adverse events. IV infusion will be administered in the clinic with staff trained in emergency care & resuscitation procedures & emergency care kit on hand during treatment & post therapy observation periods. Vital signs will be monitored at the beginning and end of the 60-minute IV infusion. Subjects will be clinically observed for at least 60 minutes (120 minutes for the lead-in phase) post-infusion during the observation period. Vitals will be measured every hour during the observation period.

If a participant experiences a Grade 2 infusion-related reaction, nursing will be instructed to pause the infusion. The infusion may subsequently resume at a slower pace of infusion, at the investigator's or clinician's discretion, and/or after symptomatic treatment (e.g., antihistamines, IV fluids). Investigators and clinicians will be instructed to discontinue IV infusions for participants who develop Grade 3 or higher infusion reactions. After infusion, study participants will be provided with investigators' contact information and asked to contact the study team if they experience subsequent adverse events, to collect unsolicited adverse events and SAEs.

Grading system from NCI CTCAE 5.0

**Grade 1:** Mild transient reaction; infusion interruption not indicated; intervention not indicated

**Grade 2:** Therapy or infusion interruption indicated but responds promptly to symptomatic treatment (e.g., antihistamines, NSAIDS, narcotics, IV fluids); prophylactic medications indicated for <=24 hrs

**Grade 3:** Prolonged (e.g., not rapidly responsive to symptomatic medication and/or brief interruption of infusion); recurrence of symptoms following initial improvement; hospitalization indicated for clinical sequelae

**Grade 4:** Life-threatening consequences; urgent intervention indicated

**Grade 5:** Death

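### No prompted check for infusion reactions between the end of the 60- or 120-minute observation period and the week 1 questionnaire, so later-onset reactions at 2,000 mg may be missed or attributed to conditioning

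*Combined protocol and SAP*

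**What the plan says.** Protocol Section 6.1.3 describes two modes of capture.

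- **Around the infusion, active.** A clinician "will assess for initial infusion reactions and record solicited adverse events". The duration is set there too: "Subjects will be clinically observed for at least 60 minutes (120 minutes for the lead-in phase) post-infusion during the observation period". Section 6.1 says of the 120-minute lead-in period, "which is increased from the 60-minute monitoring period used for the previous 20 participants who received the 500 mg dose". It allows a return to 60 minutes if the lead-in is clean.
- **Afterwards, participant-initiated.** Participants receive contact details and are "asked to contact the study team if they experience subsequent adverse events, to collect unsolicited adverse events and SAEs". Section 10.4 is consistent with this: it evaluates later unsolicited events if the team is told of them.

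Section 7 gives the prior experience at 500 mg. Infusion-related reactions "have been observed in 1% of patients treated with VIR-7831 and 1% of patients treated with placebo in COMET-ICE". The next sentence reads: "Reported events that started within 24 hours of study treatment were pyrexia, chills, dizziness, dyspnea, pruritus, rash, and infusion-related reactions". All of those events were Grade 1 or 2.

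Four other provisions bear on the point:

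- Section 10.4 records adverse events from infusion to week 36, but only SAEs and events of Grade 2 or above go on the case report form. It asks for the date of onset, not the time.
- Section 9.1 has a weekly online questionnaire that covers chest, gut, skin and general symptoms. Appendix A places the first one after infusion at day 7±3.
- Section 6.1 places infusion 1 to 7 days before conditioning.
- Appendix A, footnote C, names a day 1 blood sample. The Appendix A table has no day 1 column.

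**The concern.** The protocol's own account of earlier experience covers events with onset up to 24 hours, but active capture here stops 60 or 120 minutes after the infusion ends. A fever, rash or episode of breathlessness that starts that evening is recorded only if the participant calls, or if it surfaces later by another route. By the first scheduled prompt, on-schedule participants will generally have started conditioning. A symptom recalled then is hard to separate from conditioning effects.

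This matters because 2,000 mg is the untested part of the trial. Section 7 says there are no PK or immunogenicity data at 2,000 mg IV, and it infers the adverse event risk from lower doses. Safety is a secondary objective (Section 3.2), but Section 12.2 mentions only routine laboratory tests for it, and these are not designed to detect an infusion reaction.

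**Working it through.** **1. The prior figure.** Section 7 gives 1% on 430 treated and 438 placebo patients (430 + 438 = 868, as stated). No count is given, so the 1% cannot be reproduced exactly. If it is rounded to a whole percent, 3 to 6 events fit: 3/430 = 0.70% and 6/430 = 1.40%. The sentence states no onset window. The 24-hour window belongs to the event list that follows it.

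**2. The observed share of 24 hours**, counted from the start of a 60-minute infusion:

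- Standard: (60 + 60)/1,440 minutes = 8.3%.
- Lead-in: (60 + 120)/1,440 minutes = 12.5%.

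These are shares of clock time, not of reactions. Reactions may cluster early, and the documents do not say.

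**3. The next prompt against conditioning.** Day 7±3 runs from day 4 to day 10. Conditioning starts on days 1 to 7 after infusion. At day 4, participants with a gap of up to 4 days have reached conditioning. By nominal day 7, all who are on schedule have. The distribution of gaps is not given, and participants whose conditioning is delayed are exceptions.

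**4. Whether another route closes the gap.**

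- Questionnaire: the only action tied to its answers is blood and nasal sampling for nose or chest symptoms (Section 9.1). No text sends answers to adverse event recording.
- Record review (Section 9.1): the listed items are underlying disease, medications, infections, vaccinations, GVHD and routine laboratory tests. Infusion reactions are not listed.
- Footnote C, day 1: this is a blood sample with no symptom prompt, and the table does not show it.

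**5. What incomplete capture could cost at n = 30.** Let p be the true reaction rate and c the share captured. Both are assumptions, because the documents give neither. The expected count is 30pc, and P(at least one seen) = 1 − (1 − pc)^30.

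| True rate p | c = 100% | c = 75% | c = 50% | c = 25% |
|---|---|---|---|---|
| 1% | 0.30; 26% | 0.23; 20% | 0.15; 14% | 0.08; 7% |
| 5% | 1.5; 79% | 1.1; 68% | 0.75; 53% | 0.38; 31% |
| 10% | 3.0; 96% | 2.25; 90% | 1.5; 79% | 0.75; 53% |

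Each cell gives the expected count, then the probability of at least one. For example, with p = 5% and c = 50%, 1 − 0.975^30 = 53%.

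**6. Precision with full capture.** For zero events the one-sided 95% upper bound is 1 − 0.05^(1/n). This is 9.5% for 0 of 30 and 25.9% for 0 of the 10 lead-in participants.

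**The case against.** The strongest reply is that adverse event collection does not stop at 60 or 120 minutes. Recording runs to week 36, and the weekly questionnaire asks about the relevant organ systems. Records are reviewed on the day of infusion and weekly to week 4, and the investigator and coordinators review events at least weekly (Section 13.2). Section 10.1 names visits and interviews as sources. Some infusions are inpatient, and the observation time is a minimum. This stands to the extent that one can say reactions may be missed, not that they will be. It does not close the gap: none of these provisions is a prompt for infusion symptoms in the first days, and none is tied to recording them.

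A reader might infer more than the documents support:

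- **Bias against a 1% benchmark.** The plan is descriptive, sets no reference rate and does not call the 1% a 24-hour rate. The only rule that uses reactions is the lead-in rule on Grade 3 or higher reactions or SAEs.
- **A dose comparison confounded by observation time.** Observation time does differ between groups, but no comparison of reaction rates between 500 mg and 2,000 mg is planned.
- **The anaphylaxis case as proof of missed events.** Section 7 says "The event resolved but recurred within 2 hours", but the infusion had been stopped for it, so the first onset was during infusion. The recurrence belongs to a case already counted.
- **A numerical under-count.** Multiplying an assumed late share by an assumed unreported share gives, for instance, 0.25 × 0.5 = 12.5% to 0.5 × 0.5 = 25%. Neither fraction comes from the documents. At a true rate of 1% that loss is 0.3 × 0.125 = 0.04 to 0.3 × 0.25 = 0.08 of one event.

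It is also fair to say that a 24-hour form alone would not match the COMET-ICE event list. The case report form omits non-serious Grade 1 events, and that list includes them. The fix has to cover grade as well.

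**Conclusion.** The gap is real. After the observation period, infusion reactions are captured passively until day 7±3. By nominal day 7, on-schedule participants have reached conditioning, and no text turns questionnaire answers into adverse events. Reactions with onset up to 24 hours may therefore be missed or misattributed at 2,000 mg.

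The size of the loss cannot be derived. Near a true rate of 1% it is a fraction of one event, and the sample of 30 limits what can be learned more than the window does. Loss matters more if the rate is raised: at an assumed 5%, the chance of seeing any reaction is 79%, 68% or 53% with capture of 100%, 75% or 50%. These figures rest on assumed rates and capture shares. The point is a cheap improvement to data collection and does not threaten the primary PK objective.

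**What to change.** 1. Add one administration of the existing REDCap symptom questionnaire at about 24 hours after infusion and before conditioning starts, with time of onset for each symptom. A participant conditioned at the 24-hour minimum leaves no slack, so the form should also record when it was completed.
2. State in Sections 9.1 and 10.4 that its answers feed adverse event recording, and record infusion reactions of all grades on it.
3. In Section 12.2, report infusion reactions descriptively with exact intervals on two windows: up to 60 minutes after infusion, which all participants share, and 24 hours, for participants with the form.
4. Reconcile the day 1 entry in footnote C with the Appendix A table.

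The cost is one online form per remaining participant (at most 30), a line in Appendix A and a protocol edit. The 20 participants already dosed at 500 mg will lack the form and can appear only in the 60-minute report. This changes data collection only; no observation time, dose or clinical rule is proposed.
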